6.1.12.1. Assessment of Diarrhea/Colitis

A history of onset and duration of diarrhea, including description of number of stools and stool composition (eg, watery, bloody, nocturnal), travel history, dietary changes, and a medication review must be obtained to identify possible diarrheogenic agents.

A physical examination including assessment for fever, dizziness, abdominal pain/cramping, and weakness (ie, evaluate for sepsis, bowel obstruction, dehydration) must be performed.

6.1.12.2. Prior and Concomitant Medications

Concomitant medications will be collected within the 3 months prior to screening and during the screening period. They will also be assessed at all study visits.

6.2. Posttreatment Assessments

The EOT and EOS visits may be performed on the same day, if the subject will be discontinuing study treatment and discontinuing the study at the same time (eg, withdrawal of consent).

For subjects who discontinue idelalisib prior to IRC documented disease progression, every attempt should be made to keep the subject in the study and continue to perform regular assessments per the schedule of procedures (with the exception of PK sampling and CMV monitoring) until the subject meets criteria for study discontinuation (see Section 3.5.2).

During the follow-up period, medical treatment of the subject is left to the investigator discretion.

6.3. Assessments for Premature Discontinuation from Study

If a subject discontinues idelalisib (for example, as a result of an AE) every attempt should be made to keep the subject in the study and continue to perform the required study-related follow-up and procedures. If this is not possible or acceptable to the subject or investigator, the subject may be withdrawn from the study. It is recommended that the investigator consults with the medical monitor prior to removing the subject from study for any reason except subject withdrawal of consent.

6.4. End of Treatment

EOT assessments will be performed when a subject permanently discontinues idelalisib. For subjects who discontinue idelalisib prior to IRC documented disease progression, every attempt should be made to keep the subject in the study and continue to perform regular assessments per the schedule of procedures (with the exception of PK sampling and CMV monitoring) until the subject meets criteria for study discontinuation (see Section 3.5.2).

6.5. 30-Day Follow-Up

A 30-day follow-up visit will be performed 30 days (± 5 days) following the EOT visit; however, this visit may be waived for subjects who have permanently discontinued study drug and have had a study visit > 30 days after the last dose of study drug. Information may be gathered during a routine clinic visit, via telephone, or via another contact method.

6.6. End of Study

EOS assessments will be completed once it has been determined that the subject will discontinue the study. The EOT and EOS visits may be performed on the same day if the subject will be discontinuing study treatment and discontinuing the study at the same time (eg, withdrawal of consent).

6.7. Survival Follow-Up

Survival follow-up will be conducted at annual intervals (± 4 weeks) for 5 years, starting at the EOS visit. Information may be gathered during a routine clinic visit or other contact with the subject, or via telephone. Information gathered will include anti-tumor treatment, secondary malignancies, survival status, and death details if applicable.

6.8. Unscheduled Visits

Unscheduled visits may occur at any time while the subject is enrolled on study. Vital signs, laboratory assessments, ECG, PE, and radiographic assessments may be conducted at these visits. If the unscheduled visit is to manage an AE of interest, PK samples may be included at these visits. Data generated during an unscheduled visit will be collected on the eCRF.

7. ADVERSE EVENTS AND TOXICITY MANAGEMENT

7.1. Definitions of Adverse Events, Adverse Reactions, and Serious Adverse Events

7.1.1. Adverse Events

An AE is any untoward medical occurrence in a clinical study subject administered a study drug, which does not necessarily have a causal relationship with the treatment. An AE can therefore be any unfavorable and/or unintended sign, symptom, or disease temporally associated with the use of a study drug, whether or not the AE is considered related to the study drug. Adverse events may also include pretreatment or posttreatment complications that occur as a result of protocol-specified procedures, lack of efficacy, overdose, drug abuse/misuse reports, or occupational exposure.

An AE does not include the following:

- Medical or surgical procedures such as surgery, endoscopy, tooth extraction, and transfusion. The condition that led to the procedure may be an AE and must be reported
- Preexisting diseases, conditions, or laboratory abnormalities present or detected before the screening visit that do not worsen
- Situations where an untoward medical occurrence has not occurred (eg, hospitalization for elective surgery, social and/or convenience admissions)
- Overdose without clinical sequelae (see Section 7.6.1)
- Any medical condition or clinically significant laboratory abnormality with an onset date before the consent form is signed and not related to a protocol-associated procedure is not an AE, but rather considered to be preexisting and should be documented on the medical history case report form (CRF)

Preexisting events that increase in severity or change in nature after study drug initiation or during or as a consequence of participation in the clinical study will also be considered AEs.

7.1.2. Serious Adverse Events

An SAE is defined as an event that, at any dose, results in the following:

- Death
- A life-threatening situation (Note: The term “life-threatening” in the definition of “serious” refers to an event in which the subject was at risk of death at the time of the event; it does not refer to an event that hypothetically might have caused death if it were more severe.)

- In-patient hospitalization or prolongation of existing hospitalization
- Persistent or significant disability/incapacity
- A congenital anomaly/birth defect
- A medically important event or reaction: such events may not be immediately life-threatening or result in death or hospitalization but may jeopardize the subject or may require intervention to prevent one of the other outcomes constituting SAEs. Medical and scientific judgment must be exercised to determine whether such an event is a reportable under expedited reporting rules. Examples of medically important events include intensive treatment in an emergency room or at home for allergic bronchospasm; blood dyscrasias or convulsions that do not result in hospitalization; and development of drug dependency or drug abuse. For the avoidance of doubt, infections resulting from contaminated medicinal product will be considered a medically important event and subject to expedited reporting requirements

7.1.2.1. Protocol-Specific Serious Adverse Event Definitions

Hospital admissions for administration of the study drug, procedures required by the study protocol, or tumor-related diagnostic procedures are not considered SAEs.

7.1.3. Clinical Laboratory Abnormalities and Other Abnormal Assessments as Adverse Events or Serious Adverse Events

Laboratory abnormalities without clinical significance are not recorded as AEs or SAEs. However, laboratory abnormalities (eg, clinical chemistry, hematology, and urinalysis) that require medical or surgical intervention or lead to study drug interruption, modification, or discontinuation must be recorded as an AE, as well as an SAE, if applicable. In addition, laboratory or other abnormal assessments (eg, ECG, x-rays, vital signs) that are associated with signs and/or symptoms must be recorded as an AE or SAE if they meet the definition of an AE or SAE as described in Sections 7.1.1 and 7.1.2. If the laboratory abnormality is part of a syndrome, record the syndrome or diagnosis (eg, anemia), not the laboratory result (ie, decreased hemoglobin).

7.2. Assessment of Adverse Events and Serious Adverse Events

The investigator or qualified subinvestigator is responsible for assessing AEs and SAEs for causality and severity, and for final review and confirmation of accuracy of event information and assessments.

7.2.1. Assessment of Causality for Study Drugs and Procedures

The investigator or qualified subinvestigator is responsible for assessing the relationship to study drug using clinical judgment and the following considerations:

- **No:** Evidence exists that the AE has an etiology other than the study drug. For SAEs, an alternative causality must be provided (eg, preexisting condition, underlying disease, intercurrent illness, or concomitant medication).
- **Yes:** There is reasonable possibility that the event may have been caused by the study drug.

It should be emphasized that ineffective treatment should not be considered as causally related in the context of AE reporting.

The relationship to study procedures (eg, invasive procedures such as venipuncture or biopsy) should be assessed using the following considerations:

- **No:** Evidence exists that the AE has an etiology other than the study procedure.
- **Yes:** The AE occurred as a result of protocol procedures, (eg, venipuncture).

7.2.2. Assessment of Severity

The severity of AEs will be graded using the CTCAE, Version 5.0. For each episode, all increases in severity/grade should be reported.

If a CTCAE criterion does not exist, the investigator should use the grade or adjectives: Grade 1 (mild), Grade 2 (moderate), Grade 3 (severe), Grade 4 (life-threatening), or Grade 5 (fatal) to describe the maximum intensity of the AE. For purposes of consistency with the CTCAE, these intensity grades are defined in [Table 7-1](#).

Table 7-1. Grading of Adverse Event Severity

Grade	Adjective	Description
Grade 1	Mild	Sign or symptom is present, but it is easily tolerated, is not expected to have a clinically significant effect on the subject's overall health and well-being, does not interfere with the subject's usual function, and is not likely to require medical attention.
Grade 2	Moderate	Sign or symptom causes interference with usual activity or affect clinical status, and may require medical intervention.
Grade 3	Severe	Sign or symptom is incapacitating or significantly affects clinical status and likely requires medical intervention and/or close follow-up.
Grade 4	Life-threatening	Sign or symptom results in a potential threat to life.
Grade 5	Fatal	Sign or symptom results in death.

The distinction between the seriousness and the severity of an AE should be noted. Severe is a measure of intensity; thus, a severe reaction is not necessarily a serious reaction. For example, a headache may be severe in intensity, but would not be classified as serious unless it met one of the criteria for serious events listed in Section 7.1.2.

7.3. Investigator Requirements and Instructions for Reporting Adverse Events and Serious Adverse Events to Gilead

All SAEs, regardless of cause or relationship, that occur after the subject first consents to participate in the study (ie, signing the informed consent) and throughout the duration of the study, including the protocol-required posttreatment follow-up period, must be reported in the eCRF database and Gilead PVE as instructed. This also includes any SAEs resulting from protocol-associated procedures performed from Screening onwards.

All AEs, regardless of cause or relationship, which occur from initiation of study drug until 30 days after last administration of study drug must be reported to the eCRF database as instructed.

All special situations including pregnancy, regardless of cause or relationship, until 30 days for females or 90 days for males after last administration of study drug(s) must be reported to the CRF/eCRF database as instructed.

Any SAEs and deaths that occur after the posttreatment follow-up visit but within 30 days of the last dose of the study drug, regardless of causality, should also be reported.

All AEs should be followed up until resolution if possible. If by the last day on study (including the off-study medication follow-up period) the AE has not resolved, then the AE will be followed up until the investigator and/or Gilead determine that the subject's condition is stable. However, Gilead may request that certain AEs be followed until resolution.

Investigators are not obligated to actively seek SAEs after the 30-day period. However, if the investigator learns of any SAEs that occur after study participation has concluded and the event is deemed relevant to the use of study drug, he/she should promptly document and report the event to Gilead PVE.

All AEs and SAEs will be recorded in the eCRF database within the timelines outlined in the eCRF completion guidelines.

7.3.1. Electronic Serious Adverse Event (eSAE) Reporting Process

Site personnel will record all SAE data in the eCRF database and from there transmit the SAE information to Gilead PVE within 24 hours of the investigator's knowledge of the event. Detailed instructions can be found in the eCRF completion guidelines.

If for any reason it is not possible to record the SAE information electronically, ie, the eCRF database is not functioning, record the SAE on the paper SAE reporting form and submit within

24 hours as described above. As soon as it is possible to do so, any SAE reported via paper must be transcribed into the eCRF Database according to instructions in the eCRF completion guidelines.

If an SAE has been reported via a paper form because the eCRF database has been locked, no further action is necessary.

All AEs and SAEs will be recorded in the eCRF database within the timelines outlined in the eCRF completion guideline.

For fatal or life-threatening events, copies of hospital case reports, autopsy reports, and other documents are also to be submitted by e-mail or fax when requested and applicable. Transmission of such documents should occur without personal subject identification, maintaining the traceability of a document to the subject identifiers.

Additional information may be requested to ensure the timely completion of accurate safety reports.

Any medications necessary for treatment of the SAE must be recorded onto the concomitant medication section of the subject's eCRF and the event description section of the SAE form.

7.4. Gilead Reporting Requirements

Depending on relevant local legislation or regulations, including the applicable US FDA Code of Federal Regulations, the EU Clinical Trials Directive (2001/20/EC) and relevant updates, and other country-specific legislation or regulations, Gilead may be required to expedite to worldwide regulatory agencies reports of SAEs, serious adverse drug reactions, or SUSARs. In accordance with the EU Clinical Trials Directive (2001/20/EC), Gilead or a specified designee will notify worldwide regulatory agencies and the relevant IEC in concerned Member States of applicable SUSARs as outlined in current regulations.

Assessment of expectedness for SAEs will be determined by Gilead using reference safety information specified in the IB or relevant local label as applicable.

All investigators will receive a safety letter notifying them of relevant SUSAR reports associated with any study drug. The investigator should notify the IRB or IEC of SUSAR reports as soon as is practical, where this is required by local regulatory agencies, and in accordance with the local institutional policy.

7.4.1. Reporting of Adverse Events Relating to the Primary Endpoint and Other Anticipated Medical Events in the Study Population

Given the endpoints of the study, in order to maintain the integrity of the study, the following events that are assessed as unrelated to study drug will not be considered SAEs:

- Progression of FL
- Death related to progression of FL

Disease progression and death from disease progression should be reported as SAEs by the investigator only if it is assessed that the study drugs caused or contributed to the disease progression (ie, by a means other than lack of effect). Unrelated disease progression should be captured on the eCRF.

These unrelated events will be reported, as appropriate, in the final clinical study report (CSR) and in any relevant aggregate safety reports. The safety information from this study will also be reviewed by an independent DMC on an ongoing basis. The DMC can have access to partially blinded or unblinded data in order to determine if it is safe to continue the study according to the protocol.

7.5. Recommendations for Evaluation, Intervention, and Drug Discontinuation for Specific Adverse Events or Conditions

7.5.1. Dermatological Events

Subjects receiving idelalisib with \geq Grade 3 rash have generally presented with a maculopapular rash on the trunk and extremities that is occasionally associated with fever and/or pruritus and responded to treatment with diphenhydramine and/or topical or oral corticosteroids.

For subjects who develop a Grade \geq 3 rash for which an underlying etiology cannot be identified (eg, infection, co-suspect drug), study drug must be interrupted until Grade \leq 1; idelalisib can then be resumed at the reduced dose level, 100 mg twice daily or discontinued at the investigator's discretion.

Severe cutaneous reactions, including fatal events of Stevens-Johnson syndrome (SJS), toxic epidermal necrolysis (TEN), and drug reaction with eosinophilia and systemic symptoms (DRESS) have been reported in subjects receiving idelalisib. Assessment of potential causal association between idelalisib and the occurrence of SJS or TEN has been confounded by the coadministration of antineoplastic agents (eg, bendamustine, rituximab) and/or other concomitant medications known to be associated with SJS or TEN (eg, allopurinol). If SJS, TEN, or DRESS is suspected, idelalisib and all coadministered medications associated with SJS, TEN, or DRESS should be interrupted and the subject treated accordingly.

Subjects should be monitored for the development of SJS, TEN, or DRESS and idelalisib treatment must be permanently discontinued if such events occur.

7.5.2. Progressive Multifocal Leukoencephalopathy

Cases of progressive multifocal leukoencephalopathy (PML) have been reported following the use of idelalisib within the context of prior or concomitant immunosuppressive therapies (including fludarabine and select anti-DC20 monoclonal antibodies [eg, rituximab]) that have been associated with PML. Investigators should consider PML in the differential diagnosis in subjects with new or worsening neurological, cognitive, or behavioral signs or symptoms. If PML is suspected, then appropriate diagnostic evaluations (referral to neurologist including MRI scan preferably with contrast, cerebrospinal fluid testing for John Cunningham viral DNA) should be undertaken and treatment needs to be suspended until PML is excluded.

7.5.3. Gastrointestinal Events

Isolated cases of gastrointestinal inflammation (eg, stomatitis, colitis, cecitis) have been noted in subjects receiving idelalisib. Rare cases of gastrointestinal perforation have occurred, generally in the setting of occult carcinoma, mesenteric embolus or diverticular disease. Study treatment must be permanently discontinued in subjects who experience bowel perforation.

Subjects who have developed evidence of enteritis during idelalisib therapy have been successfully treated with antidiarrheals (eg, loperamide) and with enteric steroidal (eg, budesonide) or non-steroidal (eg sulfasalazine [Azulfidine[®]]) anti-inflammatory agents and have been able to continue or resume idelalisib.

For study subjects who develop severe abdominal pain the possibility of a bowel obstruction or perforation should be considered. Appropriate clinical and radiographic examination should be performed and supportive care or surgical intervention should be considered.

For subjects who develop persistent diarrhea, obtain history of onset and duration of diarrhea and perform a physical exam per Section 6.1.12.1.

For Grade ≥ 2 diarrhea/colitis causes may relate to concomitant medications or gastrointestinal infections. Stool collection is required per Section 6.1.5.5. Differentiate between small-bowel and large-bowel diarrhea on a clinical basis. If unclear, consider upper and lower tract endoscopy with biopsy. Refer to Section 6.1.5.6 for additional information. In the event that an infectious cause is not identified, an antimotility agent (eg, loperamide) may lessen symptoms and intervention with enteric steroidal (eg, budesonide) or non-steroidal (eg, sulfasalazine) anti-inflammatory agents should be considered. Ensure good hydration status. In such subjects, rechallenge with idelalisib at a lower dose level has resulted in recurrence of symptoms in some but not all subjects and has not been associated with other SAEs. Withhold idelalisib for subjects with Grade 3 diarrhea and monitor at least weekly until Grade ≤ 1 , then the subject may resume idelalisib at the reduced dose level, 100 mg twice daily. Discontinue idelalisib permanently for Grade 4 diarrhea.

7.5.4. Hepatic Events

Transaminase Elevations: Consistent with observations in a dog toxicology study, reversible asymptomatic alanine aminotransferase (ALT)/AST increases were also observed early in the idelalisib program in phase 1 studies (101-02 and 101-07) in subjects with hematologic malignancies. Transaminase elevations generally occurred within 4 to 12 weeks of drug initiation, and resolved spontaneously over a period of 2 to 4 weeks with drug being continued for Grade 1 and 2 elevations and drug withheld for Grade 3 or 4 elevations until resolution. These early observations have been consistent with the ongoing experience with idelalisib treatment and transaminase elevations are now well characterized as most frequently asymptomatic, transient and occurring within the first 3 months of treatment.

Grade 1 or 2 elevations commonly resolve despite continued idelalisib treatment and Grade 3 elevations must be managed by withholding idelalisib. After resolution to ≤ 1 x upper limit of normal, idelalisib may be resumed at the reduced dose level, 100 mg twice daily. Discontinue idelalisib permanently for Grade 4 elevation. There has been no evidence of impaired synthetic function. Close monitoring of hepatic laboratory tests during therapy is important to allow for appropriate idelalisib interruption and reinstatement so that subjects may continue with study drug treatment. Monitor ALT, AST, and bilirubin at least weekly until all abnormalities are Grade ≤ 1 .

Cholangitis manifest as hyperbilirubinemia out of proportion to serum transaminase elevations has been observed. While disease-related factors, neutropenia, toxicity from prior therapies, effects of ongoing supportive care, or pre-existing cholelithiasis may have initiated such events, it is possible that idelalisib played a contributory role. In such subjects, rechallenge with idelalisib has been possible and has not been associated with other SAEs.

7.5.5. Hematological and Immunological Events

In the Phase 1 experience with idelalisib in patients with NHL and CLL, subjects with Grade ≥ 3 neutropenia, anemia, and/or thrombocytopenia were enrolled to clinical trials. Decreased levels of neutrophil counts, hemoglobin, or platelet counts during idelalisib administration were largely due to minor fluctuations in these parameters among subjects with pre-existing hematological abnormalities due to disease or prior therapy. Thus, idelalisib did not appear to induce overt myelosuppression. Obvious patterns of drug-mediated reductions in circulating CD4+ lymphocyte counts or suppression of serum IgG levels were also not observed.

Treatment-emergent Grade 3 or 4 neutropenia events, including febrile neutropenia, have occurred in subjects treated with idelalisib. All subjects should have their blood counts monitored at least every 2 weeks for the first 6 months of idelalisib treatment. For subjects who develop Grade 3 neutropenia, maintain idelalisib dose and blood counts must be monitored at least weekly until ANC \leq Grade 2. For subjects who develop Grade 4 neutropenia, idelalisib must be interrupted and blood counts monitored at least weekly until ANC \leq Grade 2. Idelalisib may be resumed at the reduced dose level, 100 mg twice daily, when ANC \leq Grade 3. Neutropenia should be managed according to established clinical guidelines.

No modification of any drug for changes in circulating CD4+ counts or Ig levels is planned.

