2. CCI
3. At Grade \leq 1, may resume idelalisib at reduced dose level (100 mg BID) or discontinue at investigator discretion.

Grade 4 diarrhea or colitis

Required Actions: Discontinue idelalisib permanently.

Neutropenia

Grade 2 (ANC 1.0 to $<$ 1.5 Gi/L)	Recommended Action: Maintain idelalisib dose level and schedule.
Grade 3 (ANC 0.5 to $<$ 1.0 Gi/L)	Required Action: ANC must be monitored at least weekly until ANC Grade \leq 2. Recommended Action: Maintain idelalisib dose level and schedule.
Grade 4 (ANC $<$ 0.5 Gi/L) (or occurrence of neutropenic fever or infection)	Dosing: 
 • Required Action: Withhold idelalisib. • Recommended Action: May resume idelalisib at reduced dose level (100 mg BID) when ANC Grade \leq 3. Required Action: ANC must be monitored at least weekly until ANC Grade \leq 2. Recommended Action: Neutropenia should be managed according to established clinical guidelines.

Thrombocytopenia

Grade 2 (Platelets 50 to $<$ 75 Gi/L)	Recommended Action: Maintain idelalisib dose.
--	--

Grade 3 (Platelets 25 to < 50 Gi/L)	Required Action: Monitor platelet counts at least weekly. Recommended Action: Maintain idelalisib dose.
Grade 4 (Platelets < 25 Gi/L)	Required Actions: Interrupt idelalisib. Monitor platelet counts at least weekly. Recommended Action: May resume idelalisib at reduced dose level (100 mg BID) after platelets \geq 25 Gi/L (Grade \leq 3)

ALT=alanine aminotransferase; ANC=absolute neutrophil count; AST=aspartate aminotransferase; BID=twice daily; ULN=upper limit of normal
 a Refer to Section 6.1.5.6 for recommendations if the differentiation between small-bowel and large-bowel diarrhea is unclear.

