7.5.6. Infectious Events

Patients with lymphoid cancers receiving idelalisib have developed serious and fatal infections during therapy. Opportunistic infections, most notably PJP and CMV infection, have most frequently occurred within the first 6 months of treatment with idelalisib and are increased in the context of concurrent myelosuppressive therapy such as bendamustine.

Subjects must receive trimethoprim-sulfamethoxazole or other established prophylaxis for PJP throughout the course of idelalisib treatment. Prophylaxis must continue for a minimum period of 2 months after idelalisib discontinuation and should last for a period of 2-6 months. Prophylaxis may stop within the 2-6 months after idelalisib discontinuation when the CD4+ T-cell count is documented to be > 200 cells/mL. Prophylaxis may continue beyond 6 months at the discretion of the investigator. The duration of prophylaxis beyond the minimum requirement post idelalisib discontinuation should be based on clinical judgment and may take into account risk factors such as concomitant corticosteroid treatment and prolonged neutropenia after idelalisib treatment ends. Subjects must permanently discontinue idelalisib upon diagnosis of PJP.

CMV surveillance for active disease (quantitative PCR) must be conducted approximately every 4 weeks throughout the course of idelalisib treatment, including during drug interruptions due to toxicity or AEs. CMV viral load testing should be performed from the same specimen type whenever possible and caution should be exercised when comparing CMV viral load results across different testing centers. If unequivocal clinical or laboratory evidence of CMV infection is present, the subject must interrupt idelalisib treatment and undergo effective antiviral treatment according to established clinical guidelines. If the benefits of resuming idelalisib are judged to outweigh the risks, consideration should be given to administering pre-emptive CMV therapy.

In high-risk subjects (history of recurrent infection, allogeneic transplant, treatment with alemtuzumab, hypogammaglobulinemia) other infection prophylaxis should be considered per consensus guidelines. Administration of intravenous immunoglobulin is permitted per standard institutional practice {[Raanani 2009](#)}. For subjects who develop an infection, appropriate medical therapy should be instituted in a timely manner.

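### Section 7.5.5 tells sites to keep dosing through Grade 3 neutropenia and leaves out the mandatory hold in Table 5-2 for neutropenic fever or infection; the table's restart test also ignores the fever or infection

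*Protocol*

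**What the plan says.** Two parts of the Protocol give neutropenia dosing rules.

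- **Section 5.3.2, Table 5-2, Neutropenia.** At Grade 3 (ANC 0.5 to below 1.0 Gi/L), maintaining the dose is a recommended action and weekly ANC monitoring is required. In the Grade 4 row (ANC below 0.5 Gi/L), a parenthesis adds a second trigger by the word or: "occurrence of neutropenic fever or infection". Withholding idelalisib is a required action in that row. Restart is a recommended action: "May resume idelalisib at reduced dose level (100 mg BID) when ANC Grade" is 3 or lower.
- **Section 7.5.5.** The text acknowledges the event: "Treatment-emergent Grade 3 or 4 neutropenia events, including febrile neutropenia, have occurred in subjects treated with idelalisib". It then gives rules by grade only: "For subjects who develop Grade 3 neutropenia, maintain idelalisib dose and blood counts must be monitored at least weekly", and "For subjects who develop Grade 4 neutropenia, idelalisib must be interrupted". No dosing action is attached to febrile neutropenia or to infection during neutropenia.

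Section 7.5.6 deals with infections separately. It requires interruption for CMV and permanent discontinuation for PJP. For infections in general it says only: "For subjects who develop an infection, appropriate medical therapy should be instituted in a timely manner".

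**The concern.** A mandatory hold appears in one place, and the narrative on the same toxicity gives the opposite instruction for some of the same subjects. Neighbouring subsections restate the mandatory holds and stops of Table 5-2 for rash, bowel perforation and pneumonitis, so a site could reasonably take 7.5.5 as complete too. A site working from it could continue idelalisib through neutropenic fever or infection whenever ANC is at or above 0.5 Gi/L.

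The protocol itself shows why this matters: "Patients with lymphoid cancers receiving idelalisib have developed serious and fatal infections during therapy". Section 8.6.2 also lists Grade 3 or higher febrile neutropenia and infection among the events for additional analysis. Subjects may enter the study in the affected range, because a footnote to the laboratory eligibility table in Section 4.2 permits Grade 3 or higher neutropenia when it is due to marrow involvement.

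The second issue is restart. In the Grade 4 row, the condition for resuming does not mention the fever or infection that may have caused the hold.

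**Working it through.** No statistical formula applies. The check applies each rule to one case: **fever, judged to be neutropenic fever, at ANC 0.7 Gi/L**. By the ranges in Table 5-2 this is Grade 3, since 0.5 ≤ 0.7 < 1.0.

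| Source | Instruction for this subject |
|---|---|
| Table 5-2, Grade 3 row | Maintain (recommended); weekly ANC (required) |
| Table 5-2, Grade 4 row, fever/infection trigger | Withhold (required) |
| Section 7.5.5, Grade 3 sentence | Maintain; weekly counts; no exception |
| Section 7.5.5, Grade 4 sentence | Does not apply (ANC not below 0.5) |
| Section 7.5.6 | Hold or stop only if CMV or PJP; otherwise treat the infection |

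**Step 1: does the trigger in the Grade 4 row reach ANC 0.7?** The row gives no ANC range for neutropenic fever or infection. If the trigger applied only below 0.5 Gi/L it would add nothing, because that count already requires the hold. The word or therefore supports reading it as a separate trigger. This is an inference, though the better one.

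**Step 2: does Table 5-2 resolve its own two rows?** Yes. Section 5.3.2 says that recommended actions are guidelines, whereas the hold is required, so within the table the hold prevails. Section 7.5.5 carries no such hold to override its maintain instruction.

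**Step 3: does another section supply the hold?** Section 7.5.7 asks for interruption in serious lung events, and Appendix 8 asks the site to consider interruption or discontinuation for COVID-19. Neither covers neutropenic fever in general or other non-pulmonary infection. The reference in 7.5.5 to established clinical guidelines does not state a study-drug hold.

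**Step 4: restart.** ANC Grade 3 or better means ANC at or above 0.5 Gi/L. The subject at 0.7 meets this on the day the hold starts. Elsewhere in Table 5-2, restart is tied to the triggering event: rash, diarrhea/colitis and ALT/AST to Grade 1 or lower, and Grade 1 pneumonitis to baseline.

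**Step 5: frequency.** The documents give no count of neutropenic fever or infection at ANC ≥ 0.5 Gi/L. The nearest figures, in Section 1.3, are for subjects with FL in Study 101-09: Grade 4 or higher neutropenia in 5/72 = 6.9%, and Grade 4 or higher infections in 2/72 = 2.8%. Neither measures the affected event; they show only that the component events occur.

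**The case against.** The strongest reply is that this is an abbreviated narrative, not a conflict. The maintain instruction in 7.5.5 repeats the Grade 3 recommendation in Table 5-2. Section 5.3.1 points to Table 5-2 for dose adjustment rules, Section 3.5.1 cites it for unacceptable toxicity, and Section 7.5 is headed "Recommendations for Evaluation, Intervention, and Drug Discontinuation for Specific Adverse Events or Conditions". The mandatory wording in the Grade 3 sentence of 7.5.5 attaches to blood-count monitoring, not to maintaining the dose.

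Most of this stands as an argument about precedence: Table 5-2 should govern. It does not make the two texts agree. Section 5.3.2 also refers sites to Section 7.5 for specific events, and 7.5.5 mixes mandatory and advisory wording, so a site has to infer the precedence.

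On restart, Section 5.3.1 holds the drug for an event suspected to be related to idelalisib until it resolves or stabilizes, and only then allows reinitiation. Resumption under the row is in any case a recommendation, subject to investigator judgment, and the CMV row also leaves restart to a benefit-risk decision. This narrows the restart gap mainly to events judged unrelated, which Section 7.2.1 allows only where there is evidence of another cause. A febrile or infected subject with an identified alternative cause can fall in that group, so the gap is small but not closed. Section 1.4 says that treatment should not be started during an ongoing systemic infection. That statement concerns initiation, so it supports the restart point only by analogy.

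**Conclusion.** The concern holds, as a **minor** subject-safety wording defect. For neutropenic fever or infection at ANC 0.5 to below 1.0 Gi/L, Section 7.5.5 says maintain where Table 5-2 requires a hold. The row's restart test does not address the event that triggered the hold. The first part is the main point; the restart part is secondary because Section 5.3.1 covers much of it.

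The conclusion rests on reading the fever/infection trigger as independent of ANC below 0.5 Gi/L. If the sponsor meant otherwise, the row needs clarifying anyway. Section 7.5.13 says that the investigator's brochure contains further toxicity guidance; it was not available to check.

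The number of subjects affected cannot be derived from the documents. The same rules apply in Arms A and C, and no endpoint, estimate or between-arm comparison is affected. SAP Section 1 states that the study was terminated early, so a correction reaches only subjects still on drug.

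**What to change.** 1. In Section 7.5.5, limit the maintain instruction to Grade 3 neutropenia without fever or infection, and repeat the required hold of Table 5-2 for neutropenic fever or infection at any neutropenic count.
2. In the Grade 4 neutropenia row of Table 5-2 and the matching restart sentence in 7.5.5, allow restart at 100 mg BID only when ANC is Grade 3 or better **and** any fever or infection has resolved or stabilized.

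The change is to one table row and one paragraph, by amendment or, where permitted, a clarification letter to sites. Under Section 9.2.1, a protocol modification needs ethics committee submission and approval, and the Protocol synopsis plans about 90 centers, so administrative effort is the main cost. Some holds would be slightly longer. No extra visits or tests are needed.
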